7.5 Categorical Variables

The categorical variables used in this study are shown below (Table 10).

Table 10: Categorical Variables Definitions

Variable	Categories
BMI (kg/m ²)	Underweight: < 18.5 ¹
	Normal range: ≥ 18.5 and < 25.0
	Overweight: ≥ 25.0 and < 30.0
	Obese: ≥ 30.0
FTND total score	Mild: 0 - 3
	Moderate: 4 - 6
	Severe: 7 - 10
Daily CC consumption over the last 4 weeks as reported at Screening (per day).	<10 ¹
	10-19
	>19
ISO tar yields (mg)	1-5
	6-8
	9-10
	>10
	>10
CO breath test level (ppm)	≤ 10
	> 10
COHb level	≤ 2%
	> 2%

**Table 10: Categorical Variables Definitions**

Variable	Categories
Adverse event severity	Mild Moderate Severe
Adverse event relationship	Related Not related
Adverse event expectedness	No Yes
Action taken with study product due to adverse event	Product use interrupted Product use stopped Product use reduced Not applicable None
Outcome of adverse event	Death related to adverse event Not recovered or not resolved Recovered or resolved Recovered or resolved with sequelae Recovering or resolving Unknown
Seriousness Criteria	Fatal Life-threatening Requires hospitalization Results in disability/incapacity Congenital anomaly/birth defect
Severity of device event	Major Minor

¹ Note that due to inclusion criteria for the study there should not be any subjects underweight, or reporting <10 cig/day; therefore these categories will not be presented unless there is at least one response.

8 SAMPLE SIZE JUSTIFICATION

The following discussion addresses the ability to demonstrate on Day 5 a reduction of at least 50% on four selected primary BoExp in smokers switching from CC to THS 2.2 as compared to smokers continuing to smoke CC.

Table 11 describes the expected coefficients of variation (CV) and mean ratios (MR) between THS 2.2 and the two control arms in COHb, 3-HPMA, MHBMA and S-PMA on Day 5 based on data from a controlled, randomized, open-label, 3-arm parallel single-center confinement study that investigated exposure to selected smoke constituents in smokers switching from CCs to smoking article (SMAR) cigarettes for 5 days, the YVD-CS01-EU study (ClinicalTrials.gov: ID: NCT00812279) sponsored by PMI. The mean ratios and CVs for SMAR/CC are expected to be the same as THS 2.2/CC.

**Table 11: Coefficients of Variation (YVD-CS01-EU study)**

	THS 2.2 /CC MR (CV)	THS 2.2 /SA MR (CV)
COHb	0.40 (0.32)	2.10 (0.20)
3-HPMA	0.30 (0.50)	1.70 (0.33)
MHBMA	0.15 (0.70)	1.00 (0.35)
S-PMA	0.20 (0.70)	1.15 (0.42)

Abbreviations: 3-HPMA = 3-hydroxypropylmercapturic acid; CC = conventional cigarettes; COHb = carboxyhemoglobin; CV = coefficient of variation; MHBMA = monohydroxybutenyl mercaptyuric acid; MR = mean ratio; S-PMA = S-phenylmercapturic acid; SA = smoking abstinence; THS 2.2 = Tobacco Heating System 2.2.

Table 12 describes the expected CV and MR between THS 2.2 and the CC control arm in COHb, 3-HPMA, MHBMA, S-PMA based on data from a single-center, open-label, randomized, controlled, 2-arm parallel group study to evaluate the exposure to selected smoke constituents in smoking, healthy subjects switching from CC to THS 2.1 compared to subjects continuing to smoke CC for 5 days, the ZRHX-EX-01 study (ClinicalTrials.gov: ID: NCT01780714) sponsored by PMI. The mean ratios and coefficients of variations for THS 2.1/CC are expected to be the same as THS 2.2/CC.

Table 12: Coefficients of Variation (ZRHX-EX-01 study)

	THS 2.2 /CC MR (CV)
COHb	0.44 (0.14)
3-HPMA	0.28 (0.20)
MHBMA	0.11 (0.47)
S-PMA	0.07 (0.50)

Abbreviations: 3-HPMA = 3-hydroxypropylmercapturic acid; CC = conventional cigarettes; COHb = carboxyhemoglobin; CV = coefficients of variation; MHBMA = monohydroxybutenyl mercaptyuric acid; MR = mean ratios; S-PMA = S-phenylmercapturic acid; THS 2.2 = Tobacco Heating System 2.2.

Based on these two sets of assumptions, the power to demonstrate a reduction was computed. **Table 13** describes the expected power to demonstrate a reduction on 4 primary BoExp in smokers switching from CC to THS 2.2 as compared to those continuing to smoke CC, using one-sided test with 2.5% type I error probability using the assumptions from YVD-CS01-EU and ZRHX-EX-01 and 160 smokers (80 in THS 2.2, 40 in CC, and 40 in the SA arm).

**Table 13: Expected Power (YVD-CS01-EU and ZRHX-EX-01 Studies Assumptions)**

Assumptions	Reduction					
	50%	51%	52%	53%	54%	55%
YVD-CS01-EU	96%	91%	85%	75%	63%	48%
ZRHX-EX-01	>99%	>99%	96%	81%	48%	16%

A total of 160 smokers (80 in THS 2.2, 40 in CC, and 40 in the SA arm) will be randomized to demonstrate a reduction of at least 50% on 4 primary BoExp in smokers switching from CC to THS 2.2 as compared to those continuing to smoke CC, using one-sided test with 2.5% type I error probability.

The sample size is sufficient to obtain 95% CIs for the ratio between (geometrical) mean levels of primary BoExp in THS 2.2 and SA with upper and lower limits deviating not more than 18% from the point estimates, with an 80% overall probability of achieving the desired precision of estimating the true mean.

This study has 80% power using a one-sided test with 2.5% type I error probability:

- To detect a 0.631 [mL/min/kg] (29%) difference between THS 2.2 and CC in CYP1A2 activity, as measured by the CAF clearance, assuming a standard deviation (SD) of 0.564. Effect size and variability are derived from data obtained in the YVD-CS01-EU study sponsored by PMI.
- To detect a 24.71 [ng/g creatinine] (20%) difference between THS 2.2 and CC in 11-DTX-B2, assuming a SD of 43.78. The anticipated effect size of THS 2.2 is assumed to be about 90% of the effect of smoking cessation.

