Unless stated otherwise, all statistical tests will be two-sided and conducted at the 5% level, and all quoted confidence intervals will be two-sided 95% confidence intervals.

Sample Size:

A total of 160 subjects (80 in the THS 2.2 arm, 40 in the CC arm, and 40 in the SA arm) will be randomized. This sample size is needed to attain 80% power to show at least a 50% reduction for any of the primary BoExp in THS 2.2 compared to the CC arm, one-sided test with 2.5% type I error probability.

TABLE OF CONTENTS

SYNOPSIS.....	1
TABLE OF CONTENTS.....	14
LIST OF ABBREVIATIONS AND DEFINITIONS OF TERMS.....	19
1 INSTITUTIONAL REVIEW BOARD (IRB) APPROVAL	27
1.1 Institutional Review Board (IRB) Approval.....	27
1.2 Ethical Conduct of the Study	28
1.3 Subject Information and Consent.....	28
1.4 Good Clinical Practice and Regulatory Requirements	30
2 INTRODUCTION	31
2.1 Background.....	31
2.2 Purpose of the Study	34
2.3 Anticipated Benefits and Risks.....	34
3 STUDY OBJECTIVES.....	36
3.1 Primary Objective	36
3.2 Secondary Objectives.....	36
3.3 Exploratory Objectives	37
3.4 Study Endpoints	38
4 INVESTIGATIONAL PLAN.....	44
4.1 Overall Study Design and Plan.....	44
4.2 Rationale for Study Design and Control Groups	47
4.3 Appropriateness of Measurements.....	49
4.4 Study Duration	49
5 STUDY POPULATION	51
5.1 Selection of Study Population.....	51
6 INVESTIGATIONAL PRODUCTS	57

Confidentiality statement: Data and information contained in this document are considered to constitute trade secrets and confidential commercial information, and the legal protections provided to such trade secrets and confidential information are hereby claimed under the provisions of applicable law. No part of this document may be publicly disclosed without the written consent of Philip Morris Products S.A.

6.1	Description of Investigational Products.....	57
6.2	Use of Investigational Product.....	60
6.3	Method for Assigning Subjects to Study Arms	61
6.4	Blinding.....	62
6.5	Investigational Product Accountability and Compliance	62
6.6	Restrictions	64
6.7	Concomitant Medications	65
7	STUDY PROCEDURES	69
7.1	Informed Consent/Subject Information Sheet	69
7.2	Advice on the Risk of Smoking and Debriefing.....	69
7.3	Support for the Smoking Abstinence Arm.....	70
7.4	Clinical Assessments	70
7.5	Biomarker Assessment.....	75
7.6	Laboratory Assessments	79
7.7	Sampling Handling and Storage	81
7.8	Other Study Procedures	84
8	ADVERSE EVENTS.....	91
8.1	Definitions.....	91

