7.5.2.2 CYP1A2 activity test

CYP1A2 activity will be measured at Day 0, and at Day 5. Measurement of enzyme activity will be assessed through paraxanthine (PX) and caffeine (CAF) plasma molar concentrations approximately 6 hours (± 15 minutes) after the intake of one Tomerumin® (LionCorp.) caffeine tablet (around 170 mg caffeine) with 150 ml ± 10 ml water (Faber and Fuhr, 2004).

The exact time of intake of the caffeine tablet in the morning and of the blood sampling (blood sample will be taken 6 hours [± 15 minutes] after the intake of the caffeine tablet) must be recorded. Cytochrome P450 1A2 activity will be assessed by the measurement of the molar PX/CAF metabolic ratio (Faber and Fuhr, 2004).

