Abbreviations: 3-HPMA = 3-hydroxypropylmercapturic acid; CC = conventional cigarettes; COHb = carboxyhemoglobin; CV = coefficients of variation; MHBMA = monohydroxybutenyl mercapyuric acid; MR = mean ratios; S-PMA = S-phenylmercapturic acid; THS 2.2 = Tobacco Heating System 2.2.

Based on these two sets of assumptions, the power to demonstrate a reduction was computed. Table 18 describes the expected power to demonstrate a reduction on 4 primary BoExps in smokers switching from CC to THS 2.2 as compared to those continuing to smoke CC, using one-sided test with 2.5% type I error probability using the assumptions from YVD-CS01-EU and ZRHX-EX-01 and 160 smokers (80 in THS 2.2, 40 in CC, and 40 in the SA arm).

Confidentiality statement: Data and information contained in this document are considered to constitute trade secrets and confidential commercial information, and the legal protections provided to such trade secrets and confidential information are hereby claimed under the provisions of applicable law. No part of this document may be publicly disclosed without the written consent of Philip Morris Products S.A.

Table 18. Expected Power (YVD-CS01-EU and ZRHX-EX-01 Studies Assumptions)

Assumptions	Reduction					
	50%	51%	52%	53%	54%	55%
YVD-CS01-EU	96%	91%	85%	75%	63%	48%
ZRHX-EX-01	>99%	>99%	96%	81%	48%	16%

A total of 160 smokers (80 in THS 2.2, 40 in CC, and 40 in the SA arm) will be randomized to demonstrate a reduction of at least 50% on 4 primary BoExps in smokers switching from CC to THS 2.2 as compared to those continuing to smoke CC, using one-sided test with 2.5% type I error probability.

Power considerations related to secondary endpoints of biological changes:

The sample size is sufficient to obtain 95% CIs for the ratio between (geometrical) mean levels of primary BoExps in THS 2.2 and SA see Section 12.2 with upper and lower limits deviating not more than 18% from the point estimates, with an 80% overall probability of achieving the desired precision of estimating the true mean.

This study has 80% power using a one-sided test with 2.5% type I error probability:

- To detect a 0.631 [ml/min/kg] (29%) difference between THS 2.2 and CC in CYP1A2 activity, as measured by the CAF clearance, assuming a standard deviation of 0.564. Effect size and variability are derived from data obtained in the YVD-CS01-EU study sponsored by PMI.

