7.1.4 CYP1A2

CYP1A2 activity is calculated as the molar metabolic ratio of PX / CAF in plasma, both expressed in molar equivalent (nmol/L).

The conversion factor will be applied as follows:

PX	The molecular weight is 180.166 g/mol (Chemical Information Specialized Information Services RN:611-59-6). Therefore to convert PX in ng/mL to nmol/L the result in ng/mL is multiplied by 5.550.
CAF	The molecular weight is 194.193 g/mol. (Chemical Information Specialized Information Services RN:58-08-2). Therefore to convert CAF in ng/mL to nmol/L the result in ng/mL is multiplied by 5.150.

The converted results will be calculated to three decimal places and the ratio will be reported as a percentage with two decimal places.

If either of the PX or CAF concentration is LLOQ then the ratio will not be calculated.

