12.6.2.4 CYP1A2 Activity

CYP1A2 activity will be measured in plasma on Day 0 and Day 5. In this study the CYP1A2 activity will be calculated using the molar ratio of PX and CAF, as described in Section 7.1.4 “CYP1A2”. Descriptive statistics of the values and percent change on Day 5 from Day 0 and supportive listings will be provided.

The analysis will compare the Day 5 values between the THS 2.2 and CC arms and between the THS 2.2 and SA arms. An ANOVA model will be used with terms for sex, average daily CC consumption over the last 4 weeks as reported during screening and product. No adjustment will be made for multiple comparisons.

The SAS code will be the same as described in Section 12.6.1.1 “Primary Biomarkers of Exposure in 24 hour collection”, with no baseline value being included in the model.

LS means for each product along with the difference (THS 2.2 - CC) and 95% CI will be presented in the tables.

CYP1A2 activity will also be examined to compare the observed reductions in THS 2.2 vs. SA using the same methodology as above.

The data will be presented in the below outputs, the TFL number refers to the TFL number in the accompanying TFL shell document:

TFL number	Title
TABLES	
15.2.4.54	Descriptive Statistics of CYP1A2 Activity (%) – FAS
15.2.4.55	Analysis of CYP1A2 Activity (%) on Day 5– FAS
LISTINGS	
15.3.4.1	Listing of CYP1A2 Activity and Changes from Baseline

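### Two power statements do not follow from their own inputs: the CYP1A2 80% should be above 99.9% and concerns caffeine clearance, which the trial does not analyse, and the ZRHX-EX-01 row of the power table does not match its input table

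*SAP*

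**What the plan says.** SAP section 8 closes with two secondary power statements under one lead-in: "This study has 80% power using a one-sided test with 2.5% type I error probability". The first is "To detect a 0.631 [mL/min/kg] (29%) difference between THS 2.2 and CC in CYP1A2 activity, as measured by the CAF clearance", with an SD of 0.564 and with effect and variability taken from YVD-CS01-EU. The second is a 24.71 ng/g creatinine (20%) difference in 11-DTX-B2 with SD 43.78. Protocol section 12.2 carries the same CYP1A2 bullet: "To detect a 0.631 [ml/min/kg] (29%) difference between THS 2.2 and CC in CYP1A2 activity, as measured by the CAF clearance".

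The endpoint itself is defined differently. Protocol 7.5.2.2 states: "Cytochrome P450 1A2 activity will be assessed by the measurement of the molar PX/CAF metabolic ratio". SAP 7.1.4 agrees: "CYP1A2 activity is calculated as the molar metabolic ratio of PX / CAF in plasma". So does the analysis section, SAP 12.6.2.4: "In this study the CYP1A2 activity will be calculated using the molar ratio of PX and CAF".

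For the primary biomarkers, the plan tabulates mean ratios (MR) and CVs from two earlier studies (SAP Tables 11 and 12, protocol Tables 16 and 17). It then gives the power to show reductions of 50 to 55% on all four (SAP Table 13, protocol Table 18). For ZRHX-EX-01 the COHb input is MR 0.44, CV 0.14, and the printed power is >99, >99, 96, 81, 48 and 16%.

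**The concern.** A reader uses this section to judge what 80 versus 40 subjects can deliver. Three things do not fit.

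- An effect of 0.631 against an SD of 0.564 is more than one SD. With 120 subjects that is far beyond 80% power.
- The bullet is about a clearance in mL/min/kg. Neither document derives or analyses a clearance, so the only stated power for the CYP1A2 endpoint says nothing about the variable that will be analysed.
- The ZRHX-EX-01 power row falls more slowly, as the required reduction rises, than its printed COHb inputs allow.

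The third point bears on how much margin there is above the 50% criterion. At a 53% reduction the table suggests 81% power, while the printed inputs give 68%. ZRHX-EX-01 tested THS 2.1, the previous version of the product, and COHb is the marker that limits power.

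**Working it through.** **Inputs from the plan.** 80 THS 2.2 and 40 CC subjects; one-sided 2.5%; the MRs, CVs, differences and SDs quoted above. The factor √(1/80 + 1/40) is 0.1936. Power is from the noncentral t distribution with 118 df.

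**Method for the biomarker table.** For each marker:
- log-scale SD = √ln(1 + CV²)
- SE = SD × 0.1936
- noncentrality = ln[(1 − reduction)/MR] / SE

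Joint power is the product over the four markers, which treats them as independent.

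**Check on the YVD-CS01-EU row.** COHb MR 0.40, CV 0.32: SD = 0.3122, SE = 0.0605. At 50%, noncentrality = ln(0.50/0.40)/0.0605 = 3.69.

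| Reduction | 50% | 51% | 52% | 53% | 54% | 55% |
|---|---|---|---|---|---|---|
| Printed | 96 | 91 | 85 | 75 | 63 | 48 |
| Recomputed, joint | 95.5 | 91.4 | 84.8 | 75.2 | 62.8 | 48.5 |

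All six cells agree within one point, so this is in effect the plan's own method.

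**ZRHX-EX-01 row.** 3-HPMA, MHBMA and S-PMA have power of essentially 100% at every threshold, so COHb alone sets the row. MR 0.44, CV 0.14: SD = 0.1393, SE = 0.0270.

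| Reduction | 50% | 51% | 52% | 53% | 54% | 55% |
|---|---|---|---|---|---|---|
| Noncentrality | 4.74 | 3.99 | 3.22 | 2.44 | 1.65 | 0.83 |
| Printed | >99 | >99 | 96 | 81 | 48 | 16 |
| Recomputed | 99.7 | 97.7 | 89.2 | 67.9 | 37.2 | 12.8 |

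The 50% cell agrees. The largest gap is 13 points, at 53%.

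**Could rounding of the inputs explain it?** I searched every pair with MR 0.435–0.445 and CV 0.135–0.145 for the best fit to the 52–55% cells. It is MR 0.4375, CV 0.135, which gives 99.9, 99.1, 94.2, 78.0, 48.1 and 18.8%. The worst cells (53% and 55%) are still about 3 points off, in opposite directions. Other values in the range fit much worse: MR 0.445 with CV 0.14 gives 52.0% at the 53% reduction, 29 points below the printed 81%. A CV of about 0.12 at MR 0.44 would reproduce the row (96.1, 80.7, 47.8, 15.9), but that is a back-fit and not a value in the documents.

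**CYP1A2 bullet.**
- Noncentrality = 0.631/(0.564 × 0.1936) = 5.78, so power is 99.99%.
- Power is still 99.9% with 20% of each arm lost, and 98.0% with half of each arm lost.
- With SD 0.564, 80% power corresponds to a difference of 0.3085. The stated 29% implies a reference mean of 0.631/0.29 = 2.18, so 0.3085 is about 14%.
- For 0.631 to be detected with 80% power the SD would have to be about 1.15, twice the printed value.

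**11-DTX-B2 bullet, for comparison.** Noncentrality = 24.71/(43.78 × 0.1936) = 2.91, power 82.4%. This is close to the stated 80%, so the type of calculation is not what goes wrong for CYP1A2.

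**The case against.** The strongest reply concerns weight. The success criterion is a 50% reduction, and at 50% both rows are right. The sample size rests on that column, and no test uses the 51–55% columns or the CYP1A2 bullet. The CYP1A2 objective is descriptive. If 80% is read as at least 80%, the sentence is conservative and nobody is led to over-trust the trial. SAP version 2.0 is dated June 2014, after the planned study end of January 2014, so a correction would not have guided recruitment. All of this stands, and it limits the point to one of reporting accuracy.

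Two narrower objections also have force. The bullet says openly that it refers to caffeine clearance from another study, and CYP1A2 activity is an endpoint here; only the metric differs. That is fair, but the bullet still gives no power for the ratio that is analysed. It is also true that 11-DTX-B2 is 2.4 points off and passes as reproduced, while the best-case ZRHX-EX-01 miss is only about 3 points. However, the 3 points come from choosing the most favourable inputs in the whole rounding range. At the inputs as printed, the gap is 13 points.

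Reading 80% as a lower bound is less convincing. The wording is that of a detectable difference, and taken that way it is out by a factor of two.

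**Conclusion.** The concern holds, with limited consequences. The CYP1A2 statement is wrong as written: power is 99.99%, not 80%, and the difference detectable with 80% power is about 0.31 mL/min/kg (14%), not 0.631 (29%). It also concerns a variable the trial does not analyse. The ZRHX-EX-01 input and power tables cannot both be right as printed. The largest gap is 13 points at the printed values and at least about 3 points for any inputs that round to them. The documents do not show which table is wrong.

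This rests on a two-sample comparison on the log scale for the biomarkers and on the raw scale for CYP1A2, without covariates or dropout. The independence assumption does not matter for ZRHX-EX-01, where one marker sets the row. Power at the 50% threshold (95.5% and 99.7%), the 160 subjects, the success criterion and the analysis all stand.

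**What to change.** 1. Delete the CYP1A2 bullet in SAP 8 and protocol 12.2, or restate it as more than 99.9% power for 0.631 mL/min/kg (equivalently, 80% power for about 0.31, or 14%). If it is kept, add that it refers to caffeine clearance in YVD-CS01-EU and not to this trial's paraxanthine/caffeine ratio. A figure for the ratio needs an SD that the documents do not give.
2. Recompute the ZRHX-EX-01 row from the unrounded study values, reconcile SAP Tables 12 and 13 and protocol Tables 17 and 18, and correct whichever is wrong.
3. As a wording matter only, align the protocol synopsis, which says "This sample size is needed to attain 80% power to show at least a 50% reduction for any of the primary BoExp", with section 12.2, where power for all four biomarkers at 50% is 96% or above 99%. Calling 80% the design target would do it.

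The cost is text and table figures. Design, sample size, success criterion and analysis do not change.

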9 CHANGES FROM THE PROTOCOL SPECIFIED STATISTICAL ANALYSIS

- Shift tables for safety endpoints will not be produced for this study, the relevant information will be provided in listings.
- Statistical analysis for blood COHb (%) and exhaled CO (ppm) measurements and the QSU-brief questionnaire data, MNWS questionnaire data and the MCEQ questionnaire data will be performed including interaction terms for product and time point to enable least square means to be calculated at each time point in order to explore the pattern of the THS 2.2 effect over time. The main comparison between products will be the comparison over all time points.
- The second exploratory objective (“To evaluate in smokers switching from CC to THS 2.2, smokers continuing smoking CC and smokers switching from CC to SA the relationship between:

- Primary and secondary BoExp and NEQ
 - Selected risk markers and, primary and secondary BoExp, and NEQ
- will now only investigate:

- 1) The relationship between primary and secondary BoExp and NEQ, which will be reported in a separate report.
 - 2) The relationship between risk markers and NEQ, which will be reported in the CSR.
- The term “adjusted to creatinine” has been replaced by “adjusted for creatinine” in all relevant endpoints and analyses.

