5 STUDY OBJECTIVES AND ENDPOINTS

5.1 Primary Objective and Endpoints

1. To demonstrate the reduction of primary biomarkers of exposure (BoExp) in smokers switching from CC to THS 2.2 as compared to smokers continuing to smoke CC.

Endpoints:

- Monohydroxybutenyl mercapturic acid (MHBMA) 24-hour urine concentration adjusted for creatinine on Day 5.
- 3-hydroxypropylmercapturic acid (3-HPMA) 24-hour urine concentration adjusted for creatinine on Day 5.
- S-phenylmercapturic acid (S-PMA) 24-hour urine concentration adjusted for creatinine on Day 5.
- Carboxyhemoglobin (COHb) in blood (expressed as % saturation of hemoglobin) as measured on Day 5.

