5.5.2 Evaluation Criteria

The study will be considered successful if the study demonstrates a 50% or more reduction in MHBMA, 3-HPMA, S-PMA, and COHb in the THS 2.2 arm compared to the CC arm (as measured on Day 5), using a one-sided test with 2.5% type I error probability.

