12.6.1 Primary Analyses

12.6.1.1 Primary Biomarkers of Exposure in 24 hour collection

The primary BoExp (COHb in blood and urinary concentrations adjusted for creatinine of MHBMA, 3-HPMA and S-PMA) will be summarized as detailed in Section 12.1.3 “Descriptive Statistics”.

The baseline is as defined in Section 12.1.4 “Definitions for Statistical Data Analysis”,

The values and percent changes in the concentration adjusted for creatinine will be listed and summarized along with the COHb concentrations and percent changes from baseline. In addition line graphs will be produced for means (and 95% CI) over all timepoints.

For all arms the 24 hour urine collection will be collected daily from Day -1 to Day 5. Although the 24 hour urine collection will span into the following Day it will be reported by the day the collection started.

The primary endpoints will be log-transformed (base_e) prior to analysis. The analysis will compare (1) last Day 5 values of COHb in blood and (2) urinary concentrations of MHBMA, 3-HPMA and S-PMA corrected for creatinine on Day 5 between the THS 2.2 and CC arms. An ANCOVA (Snedecor and Cochran 1982) model will be used with terms for the log-transformed baseline value, sex, average daily CC consumption over the last 4 weeks as reported during screening and product.

The SAS code to be used is shown below:

```
Proc mixed data=_data_ ;
Class product sex cigarette_cons ;
Model log (Day 5) = log (baseline) sex cigarette_cons product ;
Lsmean product / pdiff =control('CC') alpha=0.05 cl ;
Run ;
```

The least squares (LS) means and estimate of the difference along with it's 95% CI will be back-transformed before presenting in the tables. The geometric LS means for each product along with the ratio (THS 2.2 : CC) and 95% CI will be presented in the tables.

In addition line graphs will be produced for product means (and 95% CI) over all timepoints for COHb in blood and urinary concentrations adjusted for creatinine of MHBMA, 3-HPMA and S-PMA.

The data will be presented in the below outputs, the TFL number refers to the TFL number in the accompanying TFL shell document:

TFL number	Title
FIGURES	
15.1.1.1	Blood COHb (%) Mean and 95% CI– FAS
15.1.1.2	MHBMA Urinary Concentration Adjusted for Creatinine (units) Mean and 95% CI – FAS
15.1.1.3	3-HPMA Urinary Concentration Adjusted for Creatinine (units) Mean and 95% CI– FAS
15.1.1.4	S-PMA Urinary Concentration Adjusted for Creatinine (units) Mean and 95% CI– FAS

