15.1.1.5	Blood COHb (%) % Change from Baseline Mean and 95% CI– FAS
15.1.1.6	MHBMA Urinary Concentration Adjusted for Creatinine (units) % Change from Baseline Mean and 95% CI – FAS
15.1.1.7	3-HPMA Urinary Concentration Adjusted for Creatinine (units) % Change from Baseline Mean and 95% CI– FAS
15.1.1.8	S-PMA Urinary Concentration Adjusted for Creatinine (units) % Change from Baseline Mean and 95% CI– FAS
TABLES	
15.2.3.1	Analysis of Blood COHb (%) versus CC on Day 5 – FAS
15.2.3.2	Analysis of MHBMA Urinary Concentration Adjusted for Creatinine (units) versus CC on Day 5 – FAS
15.2.3.3	Analysis of 3-HPMA Urinary Concentration Adjusted for Creatinine (units) versus CC on Day 5 – FAS
15.2.3.4	Analysis of S-PMA Urinary Concentration Adjusted for Creatinine (units) versus CC on Day 5 – FAS
15.2.3.5	Descriptive Statistics of % Change in Primary Biomarkers of Exposure on Day 5 – FAS
15.2.3.5.1	Descriptive Statistics of % Change in Primary Biomarkers of Exposure on Day 5 by Sex – FAS

TFL number	Title
15.2.3.5.2	Descriptive Statistics of % Change in Primary Biomarkers of Exposure on Day 5 by Cigarette Consumption – FAS
15.2.3.6	Descriptive Statistics of Blood COHb (%) – FAS
15.2.3.6.1	Descriptive Statistics of Blood COHb (%) by Sex – FAS
15.2.3.6.2	Descriptive Statistics of Blood COHb (%) by Cigarette Consumption – FAS
15.2.3.7	Descriptive Statistics of MHBMA Urinary Concentration Adjusted for Creatinine (units) – FAS
15.2.3.7.1	Descriptive Statistics of MHBMA Urinary Concentration Adjusted for Creatinine (units) by Sex – FAS
15.2.3.7.2	Descriptive Statistics of MHBMA Urinary Concentration Adjusted for Creatinine (units) by Cigarette Consumption – FAS
15.2.3.8	Descriptive Statistics of 3-HPMA Urinary Concentration Adjusted for Creatinine (units) – FAS
15.2.3.8.1	Descriptive Statistics of 3-HPMA Urinary Concentration Adjusted for Creatinine (units) by Sex – FAS
15.2.3.8.2	Descriptive Statistics of 3-HPMA Urinary Concentration Adjusted for Creatinine (units) by Cigarette Consumption – FAS
15.2.3.9	Descriptive Statistics of S-PMA Urinary Concentration Adjusted for Creatinine (units) – FAS
15.2.3.9.1	Descriptive Statistics of S-PMA Urinary Concentration Adjusted for Creatinine (units) by Sex – FAS
15.2.3.9.2	Descriptive Statistics of S-PMA Urinary Concentration Adjusted for Creatinine (units) by Cigarette Consumption – FAS
LISTINGS	
15.3.3.1	Listing of Primary Biomarkers

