12.6.1.2 Confirmatory Analysis

The hypothesis to be tested for each of the primary BoExp is that the geometric mean level on Day 5 of the BoExp for THS 2.2 is lower relative to CC.

Analysis of the primary BoExp will be conducted on the natural log scale. In order to test the follow hypothesis

$$\text{Null hypothesis (H}_0\text{): } m_1 \geq m_2$$

Alternative hypothesis (H_1): $m_1 < m_2$

Where m_1 and m_2 are the geometric means of the BoExp levels on Day 5 for THS 2.2 and CC respectively.

The SAS code will be the same as described in Section 12.6.1.1 “Primary Biomarkers of Exposure in 24 hour collection”.

The confirmatory analysis will be performed on the FAS only. However, if the PP and FAS differ by more than 10 subjects then the analysis will be repeated for the PP population.

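### SAP Section 9 makes an all-time-point comparison the main one for blood COHb and exhaled CO, against the Day 5 endpoint, success criterion and analyses

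*SAP*

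**What the plan says.** SAP Section 9 opens the relevant bullet with "Statistical analysis for blood COHb (%) and exhaled CO (ppm) measurements" and adds the QSU-brief, MNWS and MCEQ data. These analyses are to include product and time point interaction terms, so that least squares means can be obtained at each time point. The bullet ends: "The main comparison between products will be the comparison over all time points".

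The rest of the plan ties COHb to Day 5:

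- **Endpoint (SAP 5.1):** "Carboxyhemoglobin (COHb) in blood (expressed as % saturation of hemoglobin) as measured on Day 5". Protocol 12.4.1 agrees.
- **Success (SAP 5.5.2):** "The study will be considered successful if the study demonstrates a 50% or more reduction in MHBMA, 3-HPMA, S-PMA, and COHb", measured on Day 5 and tested one-sided at 2.5%.
- **Primary analysis (SAP 12.6.1.1):** "The analysis will compare (1) last Day 5 values of COHb in blood", with the code "Model log (Day 5) = log (baseline) sex cigarette_cons product".
- **Confirmatory analysis (SAP 12.6.1.2):** the hypothesis concerns Day 5 geometric means, and "The SAS code will be the same as described in Section 12.6.1.1".
- **Output (Table 15.2.3.1):** "Analysis of Blood COHb (%) versus CC on Day 5".

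For exhaled CO, SAP 12.6.2.1 analyses the last measurement, Table 15.2.4.10 is a Day 5 table, and the hypothesis in 12.6.2.1.1 is also a Day 5 one.

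**The concern.** Section 9 is current text whose purpose is to tell the reader where the SAP departs from the protocol. A reader who finds COHb there, with a different main comparison, can reasonably take it as overriding the protocol's Day 5 analysis. No passage says which section prevails.

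The two comparisons estimate different things. Protocol 4.2 justifies the 5-day exposure as long enough for the primary markers to reach steady state under THS 2.2 and abstinence. An average over the exposure period mixes the approach to steady state with the state itself. Levels over the exposure period already have their own secondary objective (number 2 in SAP 5.2), and that objective is descriptive.

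Success requires all four markers, so COHb is a poor one to leave with two candidate main comparisons. In an open-label study, whichever is reported could be challenged as not having been the prespecified one.

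**Working it through.** **1. Does Section 12 contain what Section 9 announces?**

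| Measure | Model in Section 12 | Time or repeated term | Inferential table |
|---|---|---|---|
| COHb | ANCOVA on log of last Day 5 value (12.6.1.1) | none | Day 5 (15.2.3.1) |
| Exhaled CO | ANCOVA on last measurement (12.6.2.1) | none | Day 5 (15.2.4.10) |
| QSU-brief | repeated-measures ANCOVA (12.6.3.1.1) | product, time point and interaction | 15.2.4.49 |
| MCEQ, MNWS | same code as QSU-brief (12.6.3.1.2, 12.6.3.1.3) | same | 15.2.4.53, 15.2.4.51 |

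The Section 9 sentence matches only the questionnaire rows. For COHb and CO it has no model, covariance structure, list of time points or table.

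**2. How many records are involved?** From the schedule notes in SAP 16.1, for Days 1 to 5:

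- COHb: one evening sample on each of Days 1 to 4 and four on Day 5, so 4 × 1 + 4 = 8.
- Exhaled CO: four tests a day, so 5 × 4 = 20.

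The endpoint record is therefore 1 of 8 for COHb and 1 of 20 for CO. If the phrase means Day 5 only, it is 1 of 4 for each. Even that narrow reading conflicts with the use of the last Day 5 value, and it brings in the morning sample taken before product use in the THS 2.2 and CC arms. These are counts of records, not weights, since the SAP does not say how time points would be combined.

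**3. Why COHb matters: reproducing SAP Table 13.** Inputs are 80 THS 2.2 and 40 CC subjects, one-sided 2.5%, and the mean ratios (MR) and CVs of SAP Table 11.

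- Log-scale SD = √ln(1 + CV²). For COHb (MR 0.40, CV 0.32) this is 0.3122.
- SE = SD × √(1/80 + 1/40) = 0.0605.
- Noncentrality = ln((1 − reduction)/MR)/SE. At 50% this is ln(0.50/0.40)/0.0605 = 3.69.
- Power is from the noncentral t with 118 df. Joint power is the product over the four markers, assuming independence.

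| Reduction to show | 50% | 51% | 52% | 53% | 54% | 55% |
|---|---|---|---|---|---|---|
| COHb alone | 95.5 | 91.5 | 84.9 | 75.3 | 63.0 | 48.9 |
| All four jointly | 95.5 | 91.4 | 84.8 | 75.2 | 62.8 | 48.5 |
| SAP Table 13, YVD-CS01-EU | 96 | 91 | 85 | 75 | 63 | 48 |

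At 50% the other markers have 99.98% (3-HPMA) and more than 99.99% (MHBMA, S-PMA). At 55%, 3-HPMA still has 99.3%. The printed row is in effect the COHb row, and it is a Day 5 calculation (SAP Section 8).

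On the ZRHX-EX-01 inputs (MR 0.44, CV 0.14), COHb has 99.7% power at 50%, consistent with the printed >99%. The 51% to 55% cells compute to 98, 89, 68, 37 and 13% against printed >99, 96, 81, 48 and 16%. That row is not relied on here.

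**4. What cannot be computed.** The documents give no COHb ratio or variance by time point, so the effect of switching comparison is unknown in size and direction.

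**The case against.** The best defence is that the operative text already settles the primary test. The endpoint, criterion, hypothesis, power basis, code, output table and topline table all say Day 5, and Section 9 cannot be run for COHb because it supplies no model. On this view, main comparison means only the product effect averaged over time within an exploratory model, as against the means at each time point. The SAP reserves the words primary and confirmatory for the success test, and Section 9 uses neither. The sentence may also have been written with the questionnaires in mind.

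Much of this stands. Section 9 is the outlier, and its intent for COHb and CO is probably supportive. But the exploratory wording attaches to the means at each time point; the next sentence calls the pooled comparison the main one. COHb and CO are named first in the bullet, and nothing subordinates their comparison to the Day 5 test.

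It is also fair that a missing model could in principle be handled elsewhere: SAP Section 3 provides for additional analyses to be described in the study report, and detailed table layouts are in a separate shell document. Even so, SAP 12.1 limits analyses to those detailed in the SAP, and 13.4 says its sections list all tables. An announced COHb and CO model with no specification or table is a gap on the SAP's own terms.

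Finally, the power figures do not change under either reading. They show which marker is limiting, not the cost of the conflict.

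**Conclusion.** The concern holds: Section 9 is wrong as written for COHb and exhaled CO. It conflicts with the Day 5 endpoint, success criterion and single-record analyses, and it announces a model that Section 12 does not contain. It should be fixed, but it does not undermine the design, because every operative passage on the primary test points to Day 5.

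No loss of power or bias is claimed. The importance rests on COHb being co-primary and, on the YVD-CS01-EU inputs, carrying essentially all the risk of failing the four-marker rule: 95.5% alone and 95.5% jointly at a 50% reduction. The joint figure assumes independence between markers, which matters little when the other three are near 100%.

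**What to change.** In SAP Section 9, limit the final sentence of the bullet to QSU-brief, MNWS and MCEQ. Then do one of the following:

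- **Keep a COHb and CO time model.** State that it is supportive, serves secondary objective 2, uses a listed set of time points, and does not replace the Day 5 ANCOVAs of 12.6.1.1 and 12.6.2.1. Add the model and its table to 12.6.2.1.
- **Drop it.** Delete COHb and exhaled CO from the bullet. Descriptive statistics and line graphs over time points are already planned for both.

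The second option is simpler and is enough if no such model will be reported. The cost is one or two sentences, plus a model and table entry under the first option. No new data are needed. SAP Section 3 requires amendments to be final before database lock, so the change belongs before that point.
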